 - Cycle 2 (to begin 2 weeks after the Cycle 2 eligibility assessment for patients with CB during Cycle 1, as long as the cumulative kidney dose remains <23 Gy [based on the dosimetry results during Cycle 1 of dose escalation])
 - Dose 1 and Safety Follow-Up Period: Week 0 to Week 3
 - Dose 2 and Safety Follow-Up Period: Week 4 to Week 11 (EOT Visit)
 - Long-term follow-up period

One treatment cycle is defined as the timeframe of approximately 12 weeks (84 days) that includes 2 administrations of the study drug given 4 weeks apart (including the 4-week Safety Follow-Up Period after Dose 1 and the Safety Follow-Up Period after Dose 2, up to Visit 11) (see [Appendix A](#)).

However, if a patient misses a dose of study drug due to study drug production problems or due to other circumstances (in certain cases), the interval between doses may be extended up to 6 weeks (Cycles 1 and 2 of both dose escalation and dose expansion phases) or up to 12 weeks (Cycles 3 and 4 of the dose escalation phase) (see [Section 3.1.5.3](#)).

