3.1.1.2 CAM-H2 administration

In the dose escalation phase, all patients will receive at least 1 cycle of CAM-H2. Patients with CB may receive up to 4 cycles of CAM-H2, as long as the cumulative kidney dose remains <23 Gy (based on the dosimetry results during Cycle 1). Cycles will be given as 2 IV administrations, 4 weeks apart. However, if a patient misses a dose of study drug due to study drug production problems or due to other circumstances (in certain cases), the interval between doses may be extended up to 6 weeks (Cycles 1 and 2) or up to 12 weeks (Cycles 3 and 4) (see [Section 3.1.5.3](#)).

Patients will be admitted to a radioactive unit for hospitalization during each IV administration for a total of 48 hours. This hospitalization can be shortened if ^{131}I decay and the patient's clearance allow discharge according to the applicable local regulations on radioactive compound exposure. Ancillary treatments to be given with CAM-H2 include thyroid-blocking drugs, premedication therapy (anti-emetic, anti-histamine, and anti-pyretic therapy), saline infusion, and amino acid infusion.

Cycle 1 will consist of the following:

- Dose 1 of CAM-H2: Visit 3 (Week 0);
- Safety Follow-Up Period: Visit 4 (Week 1), Visit 5 (Week 2), and Visit 6 (Week 3);
- Dose 2 of CAM-H2: Visit 7 (Week 4); and
- Safety Follow-Up Period: Visit 8 (Week 5), Visit 9 (Week 6), Visit 10 (Week 8), and Visit 11 (Week 11) (EOT Visit or Cycle 2 eligibility assessment).

If the patient has CB, and the cumulative kidney dose remains <23 Gy (based on the dosimetry results during Cycle 1), a second cycle may be initiated within 2 weeks after Visit 11 (Week 11) of Cycle 1, once the necessary Visit 11 (Week 11) safety follow-up assessments have been completed and reviewed. If the patient does not have CB, no further treatment will be administered and the patient will enter the long-term follow-up period.

If the patient has CB, Cycle 2 will then be initiated as follows:

- Dose 1 of CAM-H2: Visit 12 (Week 0);
- Safety Follow-Up Period: Visit 13 (Week 1), Visit 14 (Week 2), and Visit 15 (Week 3);
- Dose 2 of CAM-H2: Visit 16 (Week 4); and
- Safety Follow-Up Period: Visit 17 (Week 5), Visit 18 (Week 6), Visit 19 (Week 8), and Visit 20 (Week 11) (EOT Visit or Cycle 3 eligibility assessment).

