If the patient has CB, and the cumulative kidney dose remains <23 Gy (based on the dosimetry results during Cycle 1), a third cycle may be initiated within 2 weeks after Visit 20 (Week 11) of Cycle 2, once the necessary Visit 20 (Week 11) safety follow-up assessments have been completed and reviewed. If the patient does not have CB, no further treatment will be administered and the patient will enter the long-term follow-up period.

If the patient has CB, Cycle 3 will then be initiated as follows:

- Dose 1 of CAM-H2: Visit 21 (Week 0);
- Safety Follow-Up Period: Visit 22 (Week 1), Visit 23 (Week 2), and Visit 24 (Week 3);

- Dose 2 of CAM-H2: Visit 25 (Week 4); and
- Safety Follow-Up Period: Visit 26 (Week 5), Visit 27 (Week 6), Visit 28 (Week 8), and Visit 29 (Week 11) (EOT Visit or Cycle 4 eligibility assessment).

If the patient has CB, and the cumulative kidney dose remains <23 Gy (based on the dosimetry results during Cycle 1), a fourth cycle may be initiated within 2 weeks after Visit 29 (Week 11) of Cycle 3, once the necessary Visit 29 (Week 11) safety follow-up assessments have been completed and reviewed. If the patient does not have CB, no further treatment will be administered and the patient will enter the long-term follow-up period.

If the patient has CB, Cycle 4 will then be initiated as follows:

- Dose 1 of CAM-H2: Visit 30 (Week 0);
- Safety Follow-Up Period: Visit 31 (Week 1), Visit 32 (Week 2), and Visit 33 (Week 3);
- Dose 2 of CAM-H2: Visit 34 (Week 4); and
- Safety Follow-Up Period: Visit 35 (Week 5), Visit 36 (Week 6), Visit 37 (Week 8), and Visit 38 (Week 11) (EOT Visit).

The dose escalation phase of the study will be an open-label 3 + 3 design, where at least 3 patients are treated at each dose level. Dose escalation will be done via increases of the nominal activity of CAM-H2 in cohorts of 3 to 6 patients. The dose escalation schedule is demonstrated in [Table 3](#).

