3.1.3 Long-Term Follow-Up Period

A long-term follow-up period will start after the EOT/Early Termination (ET) Visit. Follow-up will continue for a maximum of 12 months. All patients without disease progression will be monitored every 8 weeks to evaluate PFS for a maximum of 12 months or until disease progression, death, or consent is withdrawn, whichever occurs first.

The bi-monthly visits will consist of imaging to evaluate disease status, performance status evaluation using the Eastern Cooperative Oncology Group performance status (ECOG PS), and assessment for any post-investigational treatment. Other changes in medical history or concomitant medications and AEs will be assessed. Imaging to evaluate disease status will begin 8 weeks after the last diagnostic CT scan or brain MRI performed during the study treatment period. Diagnostic CT scan will be performed in all patients. Brain MRI will only be performed in patients with known brain metastases. Patients with extracranial lesions will be evaluated for progression using RECIST version 1.1. Patients with brain metastases without extracranial lesions will be evaluated for progression using RANO-BM. Patients with extracranial lesions and brain metastases will be evaluated for progression using both RECIST version 1.1 (extracranial lesions) and RANO-BM (brain metastases). Additional details are provided in the Imaging Review Charter.

As long as there is no disease progression, imaging to evaluate disease status will be performed every 8 weeks.

For patients with disease progression or starting alternative anticancer therapy, imaging to evaluate disease status will be performed according to the local site standard of care. Review of images at this point will be done locally and not by the central imaging core laboratory. Additionally, those patients will no longer be followed every 8 weeks, but every 12 weeks, to assess survival, disease status, and post-progression therapy. Follow-up contacts (by clinic visits or telephone call) will be performed every 12 weeks until death, lost to follow-up, study end (12 months post-last patient EOT/ET Visit), or study termination by the Sponsor, whichever occurs first.

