10. Absence of any psychological, family, sociological, or geographical circumstance that could potentially represent an obstacle to compliance with the study protocol and the follow-up schedule, as determined by the Investigator. These circumstances will be discussed with the patient before enrollment in the study; and
11. Female patients of childbearing potential (ie, ovulating, premenopausal, and not surgically sterile) must have a negative pregnancy test at screening and prior to study drug administration. Patients and their partners of childbearing potential must be willing to use 2 methods of contraception, 1 of which must be a barrier method, for the duration of the study and until 6 months after study drug administration. Medically acceptable barrier methods include condom with spermicide or diaphragm with spermicide. Medically acceptable non-barrier contraceptive methods include intrauterine devices or hormonal contraceptives (oral, implant, injection, ring, or patch).

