6.5 Long-Term Follow-Up Period and End of Study

A long-term follow-up period will start after the EOT/ET Visit. Follow-up will continue for a maximum of 12 months. All patients without disease progression will be monitored every 8 weeks to evaluate PFS for a maximum of 12 months or until disease progression, death, or consent is withdrawn, whichever occurs first.

The bi-monthly visits will consist of imaging to evaluate disease status, performance status evaluation using ECOG PS, and assessment for any post-investigational treatment. Other changes in medical history or concomitant medications and AEs will be assessed. Imaging to evaluate

disease status will begin 8 weeks after the last diagnostic CT scan or brain MRI performed during the study treatment period. Diagnostic CT scan will be performed in all patients. Brain MRI will only be performed in patients with known brain metastases. Patients with extracranial lesions will be evaluated for progression using RECIST version 1.1. Patients with brain metastases without extracranial lesions will be evaluated for progression using RANO-BM. Patients with extracranial lesions and brain metastases will be evaluated for progression using both RECIST version 1.1 (extracranial lesions) and RANO-BM (brain metastases). Additional details are provided in the Imaging Review Charter. As long as there is no disease progression, imaging to evaluate disease status will be performed every 8 weeks.

For patients with disease progression or starting alternative anticancer therapy, imaging to evaluate disease status will be performed according to the local site standard of care. Review of images at this point will be done locally and not by the central imaging core laboratory. Additionally, those patients will no longer be followed every 8 weeks, but every 12 weeks, to assess survival, disease status, and post-progression therapy. Follow-up contacts (by clinic visits or telephone call) will be performed every 12 weeks until death, lost to follow-up, study end (12 months post-last patient EOT/ET Visit), or study termination by the Sponsor, whichever occurs first.

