8.4 Pregnancy Reporting

If a patient becomes pregnant during the study or within the Safety Follow-Up Period defined in the protocol, the Investigator is to stop dosing with study drug(s) immediately and the patient should be withdrawn from the study. ET Visit procedures should be implemented at that time.

A pregnancy is not considered to be an AE or SAE; however, it must be reported to Medpace Clinical Safety within 24 hours of knowledge of the event. Medpace Clinical Safety will then provide the Investigator/site the Exposure In Utero (EIU) form for completion. The Investigator/site must complete the EIU form and fax/email it back to Medpace Clinical Safety.

If the female partner of a male patient becomes pregnant while the patient is receiving study drug or within the Safety Follow-Up Period defined in the protocol, the Investigator should notify Medpace Clinical Safety as described above.

The pregnancy should be followed until the outcome of the pregnancy, whenever possible. Once the outcome of the pregnancy is known, the EIU form should be completed and faxed/mailed to Medpace Clinical Safety. If the outcome of the pregnancy meets the criteria for immediate classification as an SAE (ie, postpartum complication, spontaneous abortion, stillbirth, neonatal death, or congenital anomaly), the Investigator should follow the procedures for reporting an SAE.

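### The duty to notify a partner's pregnancy appears to end about 49 days after the last Dose 2, while contraception is required for at least 6 months after study drug

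*Combined protocol and SAP*

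**What the plan says.** Section 8.4 handles two cases. A patient's own pregnancy is reportable throughout the study as well as in the Safety Follow-Up Period. A partner's pregnancy has a narrower trigger: "If the female partner of a male patient becomes pregnant while the patient is receiving study drug or within the Safety Follow-Up Period". Notification leads to an Exposure In Utero form and, where possible, follow-up to the outcome.

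Section 8.4 refers to the Safety Follow-Up Period as something the protocol defines, but no section gives a formal definition with an end date. The label appears in the visit schedules:
- The cycle definition in Section 3.1 includes "the Safety Follow-Up Period after Dose 2, up to Visit 11".
- In Section 3.1.1.2, the Cycle 2 visits under the label finish at "Visit 20 (Week 11) (EOT Visit or Cycle 3 eligibility assessment".
- The last possible cycle of dose escalation reads "Safety Follow-Up Period: Visit 35 (Week 5), Visit 36 (Week 6), Visit 37 (Week 8), and Visit 38 (Week 11) (EOT Visit".

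What comes next has a different name. Section 3.1.3 states: "A long-term follow-up period will start after the EOT/Early Termination (ET) Visit. Follow-up will continue for a maximum of 12 months".

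Criterion 11 in Section 4.1 sets the contraception period for patients and their partners as "for the duration of the study and until 6 months after study drug administration".

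The content of long-term follow-up is given in Section 6.5: "The bi-monthly visits will consist of imaging to evaluate disease status, performance status evaluation using ECOG PS, and assessment for any post-investigational treatment". It adds: "Other changes in medical history or concomitant medications and AEs will be assessed". Neither statement mentions a partner's pregnancy.

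**The concern.** The protocol treats conception in the months after dosing as a risk to be prevented, and it names partners in that precaution. It then appears to stop requiring notification partway through the same window. A partner who conceives after the Week 11 visit but within the 6 months need not be notified to the safety group, gets no Exposure In Utero form, and is not followed to an outcome.

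The product is an iodine-131 therapeutic and men are eligible, so the situation can arise. Pregnancy outcomes not collected at the time may be hard to recover later. The stake is safety information only, because no planned analysis uses partner pregnancies.

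**Working it through.** The plan gives no figure to reproduce, so this is date arithmetic and a comparison of sections.

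**Inputs**
- The Week 11 visit is Day 50 relative to Dose 2, with dosing on Day 1 and a window of ±7 days (Tables 7 to 10, every cycle).
- The contraception period is at least 6 months after study drug (criterion 11). I take this as counted from the last administration, with 6 months = 183 days (assumption).
- Safety follow-up visits are rescheduled from the actual Dose 2 date (Section 3.1.5.3), so a delayed Dose 2 does not change the interval.

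**End of the labelled period**
- Day 50 − Day 1 = 49 days after Dose 2. Cross-check: (Week 11 − Week 4) × 7 = 49.
- With the window: 49 − 7 = 42 and 49 + 7 = 56.

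**Part of the 6 months without a partner-notification duty**
- On schedule: 183 − 49 = 134 days.
- With the window: 183 − 56 = 127 and 183 − 42 = 141 days.
- Share covered: 49 / 183 = 27%.
- Taking 6 months as 182 or 184 days moves each gap by one day.
- For a patient who stops early the gap is 183 − t, where t is the number of days from the last dose to the end of that patient's safety follow-up. The protocol does not fix t.

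**Does another section close the gap?**
- Section 8.4 says a pregnancy is neither an AE nor an SAE, so AE assessment in long-term follow-up creates no duty to report one.
- Section 8.3 ends general SAE reporting 30 days after the last dose. Later SAEs count only if judged related to study drug.
- Section 8.6 does not list pregnancy among special situations.
- The 12-weekly contacts in Section 6.5 cover survival, disease status and post-progression therapy.

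**Can existing contacts carry the question?** Counting from an end-of-treatment visit at day 49 after Dose 2:
- Every 8 weeks: 49 + 56 = 105, then 161 and 217.
- Every 12 weeks: 49 + 84 = 133, then 217.
- Switching to 12-weekly at day 105: 105 + 84 = 189. Switching at day 161: 161 + 84 = 245.

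The first contact after day 183 therefore falls at about day 189, 217 or 245, depending on when the schedule changes. Each lies inside the 12 months of follow-up.

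**The case against.** The strongest reply is that the Week 11 end date is an inference. Section 8.4 points to a defined period that the protocol never formally defines. The sentence on the patient's own pregnancy also adds that period to the whole study, which would be redundant if it lay inside the study, so a longer period may have been meant. This stands as a limit on certainty. It does not supply another end date: the label is attached only to visits ending at Week 11, and the follow-up after that has its own name.

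Section 8.4 also requires a pregnancy to be reported within a day of the site learning of it, with no time limit, and the partner sentence refers back to that procedure. The reference governs how to notify; the partner sentence sets its own window.

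A drug-related SAE remains reportable without time limit, and a congenital anomaly is an SAE criterion (Sections 8.2 and 8.3). That is a partial backstop. It depends on a relatedness judgement, and AEs are defined in the patient, so it triggers neither notification of the pregnancy nor its follow-up.

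The novelty of the product should not be overplayed. Section 1.2 calls this the first human use of the specific construct, but it also reports earlier human use, at a low radioactive dose, of the same labelled compound made by a different method.

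Two stronger readings are tempting. A reader might infer a gap of a full year, on the view that the study's duration includes each patient's 12 months of long-term follow-up. Criterion 11 does not say so, and Section 10.3 ties study end to the last patient's end-of-treatment or early-termination visit, so a year is neither a stated figure nor a true upper bound. A reader might also infer that patients' own pregnancies go unreported. They do not, because Section 8.4 covers them throughout the study.

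**Conclusion.** The point holds, for partners only. On the only labelled usage, the partner-notification window is shorter than the protocol's own 6-month contraception window by about 127 to 141 days when Dose 2 of the last cycle is given. This rests on three assumptions: the Safety Follow-Up Period ends at the Week 11 visit, 6 months is about 183 days, and the 6 months run from the last administration.

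These are uncovered days, not missed reports. The documents give no number of male patients, so a count of missed pregnancies cannot be estimated, and it is probably small. The change is worth making because it is cheap and improves safety capture, not because any result of the trial depends on it.

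**What to change.** In the partner sentence of Section 8.4, keep the on-treatment limb and replace the Safety Follow-Up limb with 6 months after the last administration of study drug. This also removes the reliance on an undefined term. A window running to study end is not needed to meet the 6-month minimum.

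Add that male patients are asked about partner pregnancy at each long-term follow-up contact already scheduled, through the first contact after month 6. The text to amend is Sections 3.1.3 and 6.5, the matching synopsis paragraphs, and the long-term follow-up footnotes to Tables 7 to 10.

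This needs one amendment and no new visits. It brings a few more pregnancy reports to follow to outcome, plus small changes to the eCRF and consent wording. No statistical figure changes.

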8.5 Expedited Reporting

The Sponsor/designee will report all relevant information about suspected unexpected serious adverse reactions (SUSARs) that are fatal or life-threatening as soon as possible to the United States Food and Drug Administration (FDA), applicable competent authorities in all the Member States concerned, and to the Central Ethics Committee, and in any case no later than 7 days after knowledge by the Sponsor/designee of such a case. Relevant follow-up information will subsequently be communicated within an additional 8 days.

All other SUSARs will be reported to the FDA, the applicable competent authorities concerned, and the Central Ethics Committee concerned as soon as possible but within a maximum of 15 days of first knowledge by the Sponsor/designee.

The Sponsor/designee will also report any additional expedited safety reports required in accordance with the timelines outlined in country-specific legislation.

The Sponsor/designee will also inform all Investigators as required per local regulation.

The requirements above refer to the requirements relating to investigational medicinal product.

Expedited reporting of SUSARs related to comparators is also required in line with the requirements above. Expedited reporting of SUSARs related to non-investigational medicinal products (NIMPs) and any other NIMPs is not required. Listings of cases related to NIMPs will be included in the Development Safety Update Report.

8.6 Special Situation Reports

Special situation reports include reports of overdose, misuse, abuse, medication error, and reports of adverse reactions associated with product complaints.

- **Overdose:** Refers to the administration of a quantity of a medicinal product given per administration or cumulatively (accidentally or intentionally), which is above the maximum recommended dose according to the protocol. Clinical judgement should always be applied. In cases of a discrepancy in the drug accountability, overdose will be established only when it is clear that the patient has taken additional dose(s) or the Investigator has reason to suspect that the patient has taken additional dose(s).
- **Misuse:** Refers to situations where the medicinal product is intentionally and inappropriately used in a way that is not in accordance with the protocol instructions or local prescribing information and may be accompanied by harmful physical and/or psychological effects.
- **Abuse:** Is defined as persistent or sporadic, intentional excessive use of a medicinal product, which is accompanied by harmful physical or psychological effects.
- **Medication error:** Is any unintentional error in the prescribing, dispensing, or administration of a medicinal product by a healthcare professional, patient, or consumer, respectively. The administration or consumption of the unassigned treatment and administration of an expired product are always reportable as medication errors, cases of patients missing doses of study drug are not considered reportable as medication error.
- **Product complaint:** Is defined as any written, electronic, or oral communication that alleges deficiencies related to the identity, quality, durability, reliability, safety, effectiveness, or performance of a drug or device after it is released for distribution. A special situations form will only be completed if a complaint is associated with an adverse drug reaction.

All special situation events as described above must be reported on the Special Situations Report form and faxed/mailed to Medpace Clinical Safety (contact information listed below) within 24 hours of knowledge of the event. All AEs associated with these Special Situation reports should be reported as AEs or SAEs as well as recorded on the AE eCRF and/or the SAE report form. Details of the symptoms and signs, clinical management, and outcome should be provided, when available.

Safety Contact Information: Medpace Clinical Safety

